#### 10.9 Indicate the MHS information system(s) from which you will seek to obtain data

If you do not know which system(s) contains the data elements you need, refer to the Guide for DoD Researchers on Using MHS Data or request guidance from an MHS data expert at: [[contact]](mailto:[contact]).

Below is a list of commonly used MHS systems. If the system from which you seek to obtain data is not listed below, list the name of the system in the "Other MHS Systems" category below **PHI Systems:**

| MHS Information System | Requesting Data |
|------------------------|-----------------|
| : AHLTA                | : Yes           |
| : ESSENTRIS            | : Yes           |

#### PII-Only Systems:

| MHS Information System | Requesting Data |
|------------------------|-----------------|
|                        |                 |

#### De-Identified Data & Other Systems:

| Information System                            | Requesting Data |
|---|-----------------|
| Other MHS System (May include PII and/or PHI) |                 |
| List other system here:                       | : Yes           |
| T-SYSTEMS                                     |                 |

#### 10.10 Do you intend to merge or otherwise associate the requested data with data from any sources outside of the MHS, including other DoD systems that are not part of the MHS?

Yes, will merge data  
 No, will not merge data

#### 10.11 Indicate the data elements about research participants or relatives, employers, or household members of the research participants that you will request from MHS hard copies or from MHS information systems.

If you will merge data, also indicate non-MHS data elements about research participants or relatives, employers, or household members of the research participants that you will have access to in any form or medium.

| Data Element(s)  | MHS                                 | Non-MHS Systems          | MHS Hard Copies          |
|--|-------------------------------------|--------------------------|--------------------------|
| 1. Names   |  |  |  |
| 2. Postal address with only town, city, state and zip code |             |  |  |

|  |                                     |                          |                          |
|--|-------------------------------------|--------------------------|--------------------------|
| 3. Postal address with all geographic subdivisions smaller than a state, including street address, city, county, precinct, zip code and their equivalent geocodes, except for the initial three digits of a zip code if, according to the current publicly available data from the Bureau of Census: 1) the geographic unit formed by combining all zip codes with the same three initial digits contains more than 20,000 people; and 2) the initial three digits of a zip code for all such geographic units containing 20,000 or fewer people is changed to 000 |             |  |  |
| 4. Dates including all elements (except year) directly related to an individual, including birth date, admission date, discharge date, and date of death   |  |  |  |
| 5. Ages over 89 and all elements of dates (including year) indicative of such age, unless you will only request a single category of "age 90 or older"   |             |  |  |
| 6. Telephone numbers   |  |  |  |
| 7. Fax numbers   |             |  |  |
| 8. Electronic mail addresses   |  |  |  |
| 9. Social Security numbers (SSNs)  |             |  |  |
| 10. Medical record numbers   |             |  |  |

|  |                          |                          |                          |
|--|--------------------------|--------------------------|--------------------------|
|  |                          |                          |                          |
| 11. Health plan beneficiary numbers  |  |  |  |
| 12. Account numbers  |  |  |  |
| 13. Certificate/license numbers  |  |  |  |
| 14. Vehicle identifiers and serial numbers, including license plate numbers                          |  |  |  |
| 15. Device identifiers and serial numbers  |  |  |  |
| 16. Web Universal Resource Locators (URLs)   |  |  |  |
| 17. Internet Protocol (IP) address numbers   |  |  |  |
| 18. Biometric identifiers, including finger and voice prints   |  |  |  |
| 19. Full-face photographic images and any comparable images  |  |  |  |
| 20. Any other unique identifying number, characteristic, or code (Diagnosis, DEERS ID, EDI-PI, Rank) |  |  |  |

If you are obtaining SSNs, provide a justification as to why and explain why a substitute cannot be used

**10.12 Do you believe it is possible for the MHS data to become identifiable because of triangulation, a small cell size, or any unique data element(s)?**

Triangulation means using different data elements that are not themselves identifiable but that when combined can be used to identify an individual. For example, triangulation would use rank and race together to determine the identity of an individual with a particular health condition.

Small cell size means that there is only a small number of eligible individuals that satisfy the category description. Guidance for acceptable cell size is available from the Centers for Medicare and Medicaid Services. For example, the rank category of four star generals with a particular

diagnosis may be less than 30, so the rank category may need to be expanded to include lower ranks.

A unique data element includes any unique features that are not explicitly enumerated in the categories of data in rows 1 – 20 of the table above (in Section 10.10), but that could be used to identify an individual. Unique data elements include characteristics that are not themselves identifying, such as the rank of general or admiral, or a race or gender, but within the context of other information could be identifiable.

- Yes, I believe there is a reasonable possibility the MHS data will become identifiable
- No, I believe there is no reasonable possibility the MHS data will become identifiable

**10.13 Have you completed and uploaded an appropriate HIPAA document ( i.e. HIPAA Authorization will be obtained or Waiver/alteration of HIPAA Authorization is being requested)?**

[figure not shown]
- Yes
- No
- N/A

**10.14 Managing Data (Data Management and/or Sharing Plan) and/or Human Biological Specimens for this Study:**

Include in this section the plan for acquiring data (both electronic and hard copy), access during the study, data/specimen storage and length of time stored, shipment/transmission, and the plan for storage and final disposition at the conclusion of the study. Describe any data agreements in place for accessing data within and/or outside of your institution (e.g., Data Sharing Agreement, Data Use Agreement, Business Agreements, etc.)

Protection and Security of Data and Identifying Information

1. Handling of paper questionnaires will be as follows:
  1. Questionnaires will be placed in trial mailbox.
  2. They will be kept in a locked box in a locked office, until they can be scanned into a secure digital folder.
2. Digital protection:
  1. Data will be stored in accordance to Navy HRPO policy and data storage policies
  2. Password protection: Each patient will be assigned a subject identifier during randomization. This file will be password protected.
    1. The data will remain on a study team member's computer which is only accessible with a CAC card.
  3. De-Identification: Only subject identifiers will be used in psychometric testing. Additionally, as shown in Figure 2, the subject identifier will be the only means to connect to various data related to the subject. The Subject identifier will be stored separate from all de-identified information.
  4. Separation of data: Data collection sheets will be separated into different files, as shown in Table 3.

**Figure 2:** Subject Identifier connection to other data sheets for a participant

**Table 3:** Security Management breakdown of Data Collection Sheets

| Spreadsheet            | Contents  | Who has access?     | Security           |
|------------------------|---|---------------------|--------------------|
| Subject Identifier key | Subject identifier code & Patient name  | NMCCL Investigators | Password protected |
| Demographics           | Email, gender, DOB, age, number of previous attempted suicide, history of self-harm, psychiatric history, | Only Investigators  | Separate file      |

|       |  |                    |               |
|-------|--|--------------------|---------------|
|       | recent antidepressant use, current psychotropic medication, classification (military/civilian) |                    |               |
| LOS   | Time of admission & transfer   | Only Investigators | Separate file |
| BSSI  | BSSI results   | Only Investigators | Separate file |
| MADRS | MADRS results  | Only Investigators | Separate File |

(6) Disposition of Data and Identifying Information at End of Project

Specified data will be stored digitally in accordance to Navy regulation. All other documents will be disposed per Navy Instruction at the conclusion of the storage period. In accordance to DHHS protection of human subject's regulation, IRB activities and records will be maintained in digitally secure location for at least three years (45 CFR 46.115(b)). In accordance to HIPAA requirements, data that fall under this regulation will be stored for at least six years.

**10.15 Managing Data (Data Management and/or Sharing Plan) and/or Human Biological Specimens for Future Research:**

If the study involves collecting, storing, or banking human specimens, data, or documents (either by the Investigator or through an established repository) for FUTURE research, address. How the specimens/data will be used, where and how data/specimens will be stored (including shipping procedures, storage plan, etc.), whether and how consent will be obtained, procedures that will fulfill subjects' request as stated in the consent, whether subjects may withdraw their data/specimens from storage, whether and how subjects may be recontacted for future research and given the option to decline, whether there will be genetic testing on the specimens, who will have access to the data/specimens, and the linkage, the length of time that data/specimens will be stored and conditions under which data/specimens will be destroyed.

n/a

**11.0 Statistical/ Data Analysis Plan**

**11.1 Statistical Considerations:**

List the statistical methods to be used to address the primary and secondary objectives, specific aims, and/or research hypotheses. Explain how missing data and outliers will be handled in the analysis. The analysis plan should be consistent with the study objectives. Include any sub-group analyses (e.g., gender or age group). Specify statistical methods and variables for each analysis. Describe how confounding variables will be controlled in the data analysis

**STATISTICAL ANALYSIS**

All data analysis will be carried out using SPSS ® Version 25. Tableau Desktop 2018.1 will be used to augment the creation of graphs. See 3.7.C for power calculation and sample size derivation. If subjects do not complete a baseline, they will not be incorporated in the analysis. A recent clinical study validated that an average of four items from the SSI, with a cut-off of  $\geq 2$ , is sufficient in classifying patients as high risk vs. low risk. Therefore, any patient who does not complete at least four items on the SSI during each of the post administration time points will be excluded from the study. Missing data will be excluded from analysis as long as the degree of freedom permits. The type of data analysis will be in accordance to the Test plan, Table 6. Each arm of the trial will be considered a "group." Appendix D: Sample Data Collection Sheet describes demographic data points as well as measurement scale of each of the below variables. Stratification factors will be accounted for as a covariate in multivariate models.

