The BSSI will measure the severity of SI. It is based on the interviewer rated version of the original Scale for Suicidal Ideation (SSI), which is one of the few document suicide assessment tools with predictive validity for suicide completion.42 The internal reliability, test and retest validity, as well as invariance over time has been demonstrated for the BSS. 43, 45 Furthermore, the first five items of the BSSI are a common clinical screening for the presence of suicidal thoughts.40 For these reasons, the BSSI was chosen as our primary outcomes measure. Two studies have indicated that the cut off between high and low risk is a BSS  $\geq 2$ .43, 45 A recent investigation has determined BSSI  $\geq 6$  is predictive of future suicide attempts. 53 These two values will serve in our analysis.

The Montgomery- Åsberg Depression Rating Scale (MADRS) is a widely known 10 item clinician administered measure of depression severity.46 Since its development in the late 1970s, it has become more popular than the gold standard, Hamilton rating scale for Depression (HAM-D). It is considered to be more sensitive to change, just as effective, and simpler to use clinically.47 However, the reliability depends on good interrater agreement.48 Difficulties in clinical trial to show signal detection for known effective drugs have implicated clinician administered measurement as a possible source of error. To avoid poor interrater reliability, rater bias, and variable interview quality,48 this trial will utilize the self-administered version of the MADRS-S.49 This has 9 items and

a total score ranging from 0 to 27.50 The scoring of MADRS-S has shown to be similar to that of physician scoring.

The emotional pain of the suicidal patient requires empathetic care that may not always be possible with the time pressures, volume, and pragmatic nature of the ED environment. A pharmacologic intervention with rapid effects to decrease SI would play a vital role in improving the standard of care for this vulnerable population.

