### 11.6 Data Analysis Plan: Complete description: Background, Objectives, Design, Step by Step how the project is going to be done, Data analysis plan:

**Table 6:** Test Plan of Data Analysis

| Question to be answered   | Type of Analysis                                   | Independent (x)  | Dependent (y)      | Relationship     |
|---|--|--|--------------------|------------------|
| Is there a difference effect of ketamine in those who are high suicide vs. high depressed?                  | McNemar test                                       | High Suicide   | High depressed     | Within           |
| Is there a difference in the placebo between the same two groups?   | McNemar test                                       | High Suicide group                                     | High Suicide group | Within           |
| Is there any difference between ketamine vs. placebo on BSSI & MADRS?                                       | One-way MANOVA                                     | Group  | BSSI; MADRS        | Between          |
| Is there a difference in SI between Ketamine vs placebo   | 2 Independent sample t test                        | Group  | BSSI @ T4          | Between          |
| Is there a difference in depression between Ketamine vs placebo   | 2 independent sample t test                        | Group  | MADRS @ T4         | Between          |
| Is there a difference in effect from placebo when accounting for covariates?                                | MANCOVA  | Fixed factor: Group
Covariates: Demographics        | BSSI, MADRS @ T4   | Between          |
| Is there a difference in effect from ketamine @ the different time points?                                  | Mixed model
Or
Repeated measure ANOVA | Fixed factor: Group                                    | BSSI               | Within & between |
| Is there a difference in group at the different time points, when MADRS is a covariate?                     | Mixed model                                 | Fixed factor: Group
Covariates: MADRS               | BSSI               | Within & between |
| Is there a difference in group at the different time points, when MADRS, and demographics are considered? * | Mixed model                                 | Fixed factor: Group
Covariates: MADRS, demographics | BSSI               | Within & between |

\*This case requires a larger sample size.

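### The four-item minimum for a usable BSSI form rests on evidence for a high/low call only, yet the same forms feed the continuous score and the ≥6 cut-off, with no scoring rule for blanks

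*Combined protocol and SAP*

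**What the plan says.** The Statistical Analysis text in section 11.1 starts from evidence: "A recent clinical study validated that an average of four items from the SSI". At a threshold of 2 or more, this number of items, it says, "is sufficient in classifying patients as high risk vs. low risk". From this it draws a rule that removes from the study "any patient who does not complete at least four items on the SSI during each of the post administration time points". Keeping forms with four or more answers is implied by this rule, not stated outright. The rule says SSI; section 9.3 treats BSS, BSSI and SSI as names for the same primary measure.

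The only other missing-data rule in that section, apart from excluding subjects without a baseline, is "Missing data will be excluded from analysis as long as the degree of freedom permits".

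On how the scale is used:
- Section 9.2 says "The BSSI will measure the severity of SI". It names cut-offs of 2 and of 6 and adds "These two values will serve in our analysis".
- Section 9.2 also says "the first five items of the BSSI are a common clinical screening for the presence of suicidal thoughts", so a form with four answers is incomplete.
- Table 6 in section 11.6 compares the arms on BSSI by "2 Independent sample t test". It also uses BSSI as a dependent variable in a MANOVA, a MANCOVA and mixed models or a repeated-measures ANOVA. BSSI is not dichotomised in any of these rows.

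**The concern.** A rule that is adequate for sorting patients into two groups is being used to decide which forms can supply a severity score. These are different demands. A high/low call may be settled after a few items, whereas a total depends on all of them.

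Two details weaken the support further. If the cited average is the number of items needed, it is not a minimum: unless every patient needed exactly four, some needed more. And the evidence is tied to the cut-off of 2, so it says nothing about the cut-off of 6.

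At stake is the main between-arm comparison of suicidal ideation. With no stated scoring rule, the value assigned to a partial form could be settled after the data are seen, and the options give different answers. The forms are completed on paper by acutely suicidal patients in the ED or on a psychiatric ward, so skipped items are plausible, although the documents do not say how common they would be.

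**Working it through.** **The plan's own figure.** The sample size does not depend on this point, and it reproduces. A two-sided two-sample t test at alpha 0.05 and power 0.80 gives 25.52 per group for d = 0.8 (stated 25.5). A correlation of 0.5 (my assumed value for large) gives 28.25 (stated 28.2). Then 2 × 28 = 56 and 56 × 1.1 = 61.6, or 62 as stated; 56/0.9 = 62.2 is close to it.

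**Evidence against use.**

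| Use of the form | Where planned | Covered by the four-item evidence? |
|---|---|---|
| High/low at ≥2 | 9.2 | Yes, as the plan describes it |
| High/low at ≥6 | 9.2 | No, different cut-off |
| Continuous score | 9.2, Table 6 | No |

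**Size if blanks add nothing to a sum.** The number of items K is not in the documents, so it is assumed. At equal item scores, a four-answer form shows 4/K of the total and understates it by 1 − 4/K:
- K = 10: 1 − 0.40 = 60%
- K = 19: 1 − 0.21 = 79%
- K = 21: 1 − 0.19 = 81%

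K = 5, the fewest that section 9.2 allows, would give 20%. These are the worst retained forms. A form missing one item of 19 loses 1/19, about 5%.

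Effect on an arm mean, assuming K = 19, mean item score 1 and 28 patients per arm (56/2):
- two four-answer forms: 2/28 × (19 − 4) = 1.07 points
- four such forms: 4/28 × 15 = 2.14 points

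**Effect on the comparison.** This is an illustrative simulation in which every input is assumed: 19 items scored 0 to 2, 28 per arm, arm means 15.18 and 9.17, difference 6.01, d about 0.85. Each partial form has exactly four answers.

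| Partial forms (each arm) | Zero-filled: difference, power | Prorated: difference, power |
|---|---|---|
| 0% | 6.08, 0.88 | 6.04, 0.87 |
| 10% | 5.58, 0.79 | 6.07, 0.86 |
| 20% | 5.03, 0.69 | 6.11, 0.85 |

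The shrinkage agrees with simple arithmetic, where the difference is multiplied by 1 − q(1 − 4/K) for a proportion q of partial forms. At 10%, 6.01 × (1 − 0.10 × 0.789) = 5.54. At 20%, 6.01 × (1 − 0.20 × 0.789) = 5.06.

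With unequal rates (10% and 30%), no true effect and zero-filling, the expected spurious difference is 15.2 × (0.30 − 0.10) × 0.789 = 2.40 points. The simulation gave 2.42, and the t test rejected in about 19% of trials instead of 5%.

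**If forms are prorated.** The mean of the answered items times K has no expected bias when items are exchangeable, which is how the simulation was built. If the answered items differ systematically from the rest, the bias can go either way. A score built from four items is also less precise, hence the small loss of power in the last column.

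**The case against.** A reader might infer that the plan scores incomplete forms as improvement, so that suicidal ideation will be understated. The documents do not support that. They give no item-level scoring rule, and "Missing data will be excluded from analysis as long as the degree of freedom permits" could refer to the item, the score or the case. Zero-filling is one possible reading. Under proration the expected understatement is zero with exchangeable items, and if incomplete scores are dropped there is none. Appendix D, which is said to hold the sample BSSI and each variable's measurement scale, is not in the available text and may contain a rule.

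A reader might also infer that lingering drug effects at 4 hours would make ketamine patients skip items. That fits the protocol poorly. The risk table in section 14.1 has dissociative symptoms gone within two hours, before the earliest 4 (±1) hour questionnaire, and Hypothesis 1 concerns 24 hours. As-needed benzodiazepines for ketamine side effects (sections 14.1 and 14.2) are a possible route to unequal completion, but no more than possible.

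It is also fair to say that classification is a planned use. The cut-offs are named in section 9.2 and Table 6 has McNemar tests on high-suicide groups, so the rule has a coherent purpose at the cut-off of 2. The item count and the frequency of partial forms are assumed throughout.

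All of this limits the claim about direction and size. It does not supply support for four items as the minimum for a continuous score or for the cut-off of 6.

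**Conclusion.** The point holds as a mismatch between the stated evidence and its main use, combined with an unspecified scoring rule. In effect the plan admits post-dose forms with as few as four answers, on evidence that reaches only the ≥2 classification. The value such a form contributes to the continuous analyses is undefined in the available text.

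Direction and size are conditional. Understatement of 60% to 81% per four-answer form needs three assumptions: blanks add nothing to a sum, the scale has 10 to 21 items, and items score equally. Under zero-filling, partial forms that are equally common in both arms shrink the difference and cost power; unequal rates bias the comparison. Under proration from four items, the score is imprecise and is unbiased only if items are exchangeable. The mismatch should be corrected before the data are analysed, because the correction is cheap and removes a choice that could otherwise be made after the results are seen.

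**What to change.** In section 11.1:
1. Limit the four-item minimum to the classification at ≥2.
2. For the continuous BSSI score and the ≥6 cut-off, require a complete form. Alternatively, prorate (mean of answered items times number of items) only when no more than a small, prespecified number of items is missing.
3. Below that minimum, set the score for that visit to missing and keep the patient in the study.
4. Add a sensitivity analysis restricted to complete forms.
5. If the mixed model is meant to use the patient's other visits, commit to it at the planned 62 subjects. Section 11.5 now makes the linear model for repeated measures conditional on reaching 74.

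The cost is a few sentences and one extra analysis. The downside is that a few more visit scores become missing. The single-time-point t test would lose those patients, which is why item 5 matters.

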#### Primary outcome:

**Specific aim 1:** The objective of this investigation is to identify the clinical effectiveness of sub-dissociative dose IV Ketamine as an adjunctive treatment for the acutely suicidal patient in the ED.

**Hypothesis 1:** There will be a clinically significant decrease in suicidal ideation (SI) in those treated with Ketamine after 24 hours.

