#### Secondary outcomes:

**Specific aim 2:** Determine if this protocol for ketamine holds its effectiveness over time post infusion.

**Hypothesis 2:** The effects of ketamine can last up to a week post infusion.

Primary outcome measures of SI will be through self-administered Beck Scale for Suicidal Ideation (BSS or BSSI or SSI). The self-administered version of Montgomery- Åsberg Depression Rating Scale (MADRS) will be used to measures degree of concomitant depression symptoms. These patient-level data will serve as baseline comparatives. Subjects shall be randomized by the pharmacy and designated to either ketamine treated or saline placebo arm, with both the treating nurse and physician blinded. The experimental arm shall receive 0.5 mg/kg IV ketamine infusion over 40 minutes. To test for effectiveness within groups, we will measure outcomes at two different time points, 4 and 24 hours post infusion. To evaluate effectiveness between groups we will compare results between treatment and placebo arms. To test for specific aim 2, and to maximize response rate, a phone call will be made, one week after the initial questionnaire was done.

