A Linear model will be used for analysis of repeat measures if sample size reach 74 subjects. This model accounts for uneven spacing in repeated measures, accounts for random effects, will provide a greater flexibility in analysis. The ability of this analysis is limited by the degree of freedom, which is influenced by the sample size. R separates the F test into two variables representing the degree of freedom of the model and error, which are the numerator and the denominators in the F test. In this test, the numerator (u) is the number of observations, and is equal to  $p - 1$ , where  $p$  is the number of predictors (sex, age, etc....). The denominator (v) is the degree of freedom of the error and is equal to  $n - p$ , where  $n$  is the number of observations, or, in our case, subjects. Sample Calculation 1 was used to determine  $n$  need to power a model that would take into account three to five predictors. (Table 5)

Sample Calculation 1:

$$u = p - 1 \rightarrow u + 1 = p$$

$$v = n - p \rightarrow v + p = n$$

To solve for  $n$ :

$$v + u + 1 = n$$

**Table 5:** N needed to power Linear model with a large effect size ( $f^2 = 0.35$ )

| Numerator (u) | Denominator (v) | n | 2n |
|---------------|-----------------|---|----|
|               |                 |   |    |

|   |    |    |    |
|---|----|----|----|
| 5 | 37 | 43 | 86 |
| 4 | 34 | 37 | 74 |
| 3 | 31 | 35 | 70 |

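### Read plainly, the SSI completeness rule lets a missed one-week call delete a valid 24-hour result

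*Combined protocol and SAP*

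**What the plan says.** Section 11.1 (Statistical Analysis) contains three rules on incomplete data:

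- Baseline: "If subjects do not complete a baseline, they will not be incorporated in the analysis".
- After infusion: whoever "does not complete at least four items on the SSI during each of the post administration time points will be excluded from the study".
- Otherwise: "Missing data will be excluded from analysis as long as the degree of freedom permits".

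Section 10.1 sets three post-infusion assessments for both arms: 4 hours, 24 hours (window 24–36 hours) and one week, the last by phone.

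Section 9.3 ties 24 hours to the primary hypothesis: "There will be a clinically significant decrease in suicidal ideation (SI) in those treated with Ketamine after 24 hours". The one-week contact is secondary: "To test for specific aim 2, and to maximize response rate, a phone call will be made".

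For the repeated measures, section 11.5 says "A Linear model will be used for analysis of repeat measures if sample size reach 74 subjects". Sections 11.2–11.4 plan 62 patients, 31 per arm. In Table 6 (section 11.6), the row on BSSI at the different time points offers a mixed model or "Repeated measure ANOVA". The footnote "This case requires a larger sample size" is attached only to the row with MADRS and demographics.

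Section 13.6, quoting the consent form, says that the data of patients who withdraw stay in the analysis.

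**The concern.** Four items at each point means four items at every point, and the stated consequence is removal from the study, not from a visit or an analysis. A missed phone call is zero items at one of the three points. A patient with complete 4-hour and 24-hour forms would therefore be lost to the primary comparison because of a later contact that serves only the secondary aim.

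Two things are at stake. The first is selection: inclusion in the 24-hour comparison would depend on something that happens after randomisation and after the outcome is measured. If the chance of missing the call depends on suicidal ideation, and does so differently by arm, the 24-hour estimate is biased. The second is power: losses accumulate over three visits, although only one visit is being tested.

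The reason given for the rule is that four items are enough to classify risk. That supports checking whether each form is usable. It gives no reason to discard a usable 24-hour form.

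**Working it through.** **Inputs from the plan.** Section 11.5 and Table 4: significance level 0.05, power 0.80, d = 0.8, 25.5 per arm, 28.2 per arm for a large correlation, 10% dropout. Section 11.4: 31 per arm.

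**Reproducing the plan's figures.** A two-sided two-sample t-test (noncentral t) at d = 0.8 and power 0.80 needs 25.52 per arm, the 25.5 of Table 4. A correlation of 0.5 (assumed to be what the plan calls large) needs 28.25, against the plan's 28.2. About 56 in total × 1.1 = 61.6, rounded up to 62. The stated sample size reproduces.

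**Power formula.** With n per arm, the noncentrality is d × √(n/2) on 2n − 2 degrees of freedom. At n = 31 this is 0.8 × √15.5 = 3.15 on 60 degrees of freedom, giving power 0.873. The test is taken at 24 hours, the time point of Hypothesis 1.

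**How many exclusions are tolerable.** Power 0.80 needs 2 × 25.52 = 51.05 patients, a loss of 1 − 25.52/31 = 17.7%. Ten exclusions leave 52 (power 0.807); the eleventh leaves 51 (0.7996).

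**Case A: only the one-week call is missed; all 4-hour and 24-hour forms are valid.** Loss rates are assumed.

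| Calls missed | Kept under the rule as written | Power | Kept under a visit-level rule | Power |
|---|---|---|---|---|
| 10% | 62 × 0.90 = 55.8 | 0.835 | 62 | 0.873 |
| 20% | 62 × 0.80 = 49.6 | 0.788 | 62 | 0.873 |
| 30% | 62 × 0.70 = 43.4 | 0.730 | 62 | 0.873 |

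**Case B: 10% missed at each of the three visits (assumed).** A visit-level rule keeps 62 × 0.90 = 55.8 at 24 hours (power 0.835). What the rule as written keeps depends on how far the same patients miss several visits. Correlated misses use a Gaussian copula with a common correlation.

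| Overlap of misses | Proportion kept | Patients | Power |
|---|---|---|---|
| Independent | 0.9³ = 0.729 | 45.2 | 0.748 |
| Latent correlation 0.5 | 0.782 | 48.5 | 0.778 |
| Latent correlation 0.9 | 0.850 | 52.7 | 0.813 |
| Complete overlap | 0.900 | 55.8 | 0.835 |

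**Repeated-measures row.** Rewording section 11.1 alone does not settle this row. With 62 planned and a condition of 74, section 11.5 rules out the linear model. The alternative in Table 6, repeated measures ANOVA, in its standard form drops any patient with a missing visit, so the same loss returns. The 74 is 2 × 37, the Table 5 line with u = 4, which by that section's own formula p = u + 1 is a model with five predictors. The Table 6 row on BSSI over time lists group as its only fixed factor and does not carry the larger-sample footnote.

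**The case against.** The strongest case is that the rule was meant by visit. It follows from a statement about how many items make a form usable, and the next sentence, on excluding missing data, has less to do if anyone short at one visit is already out. Section 13.6 also suggests that partial data were meant to be used. All this is fair, and under that reading the losses above do not arise in the 24-hour comparison. But no section states a visit-level rule, the next sentence could equally cover MADRS or covariates, and the text says the patient leaves the study.

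On size, the only loss rate in the plan is 10%, and at 10% power stays above target. Section 11.5 does not limit that 10% to 24 hours, so it may already include one-week losses. A 10% loss at 4 and 24 hours may be too high, since patients are then in the ED or the psychiatric unit. Section 10.2 also plans email authorisation for the one-week follow-up, so the phone may not be the only route. These points stand: no power shortfall is demonstrated, only its range under assumptions. The bias is likewise conditional and not quantified.

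Table 6 labels its single BSSI t-test T4, which Table 2 (t0 to t3) does not define, so placing the test at 24 hours rests on Hypothesis 1. That also stands, and it is a reason to name the time point. Finally, Table 6 lists the mixed model first for the time-point row, so ANOVA is not clearly the default; sections 11.5 and 11.6 disagree and need to be aligned.

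**Conclusion.** The concern holds on the plain reading of section 11.1 and should be fixed before analysis. A valid 24-hour result would be deleted because of a later, secondary contact, and the primary comparison would be conditioned on a post-randomisation event. That flaw does not depend on any assumed loss rate.

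The cost in power does. At d = 0.8 it falls from 0.87 to between 0.835 and 0.73 when 10% to 30% miss only the call. With 10% missed at each visit it is 0.75 if misses are independent, against 0.835 under a visit-level rule, and the gap closes as misses overlap. If losses are unrelated to the score, only power is affected.

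Section 13.6 does not define an analysis set, but it sits uneasily with the exclusion and should be reconciled with it. If a visit-level rule was intended, one sentence in section 11.1 settles the 24-hour comparison.

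**What to change.** **Section 11.1.** Replace the patient-level exclusion with a visit-level rule, for example:

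> A BSSI form that fails the completeness rule is treated as missing for that visit only. The primary comparison is the 24-hour (t2) BSSI in all randomised patients with a baseline and a valid 24-hour form, whatever happens at 4 hours or one week. The existing rule in section 10.1 for patients whose infusion is stopped still applies.

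This keeps the baseline rule and leaves section 10.1 unchanged. The stopped-infusion rule is also a post-randomisation exclusion; this change does not address it.

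**Section 11.6, Table 6.** Replace the undefined T4 with a named time point, so that one row tests Hypothesis 1 at 24 hours.

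**Sections 11.5 and 11.6.** For the row on BSSI at the different time points, specify the mixed model on all available visits and remove the 74-subject condition for that row.

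**Section 13.6.** Check that the statement on withdrawn patients' data agrees with the new wording.

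The cost is a few sentences of SAP text and slightly more analysis work. No patients or visits are added.
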